Concerning more specifically the rate of failure in GTR, clinical publications concerning the use of resorbable membrane, generally in association with bone substitute grafting for filling the defect, can be cited. Merli et al [12] report an analysis of 65 full text articles: they report only one publication with 396 patients and all the others concerned limited sample size studies. All these studies report successfull results for tissue regeneration at implant dehiscences and fenestration with membranes for GTR.

Several articles specifically report a failure in tissue regeneration, with RCM covering the defect to assure barrier effect, cells of bacterial infiltration, promoting the mucosa regeneration and protecting the bone ingrowth under the membrane. The following studies report similar success :

Publication	Percentage of soft tissue healing
Wessing et al [20]	100 %
De Angelis et al [3]	88.5 %
Felice et al [5]	100 %
Merli et al [11]	100 %
Taschieri et al [17]	81.2 %
Taschieri et al [18]	89.5 %
Meloni et al [10]	87 %

Table 1 Justification of the percentage of soft tissue healing

Authors' conclusions

GTR has a greater effect on probing measures of periodontal treatment than OFD, including improved attachment gain, reduced pocket depth, less increase in gingival recession and more gain in hard tissue probing at re-entry surgery. However there is marked variability between studies and the clinical relevance of these changes is unknown.

There is therefore little value in future research repeating simple, small efficacy studies. The priority should be to identify factors associated with improved outcomes as well as investigating outcomes relevant to patients. Types of research might include large observational studies to generate hypotheses for testing in clinical trials, qualitative studies on patient-centred outcomes and trials exploring innovative analytic methods such as multilevel modelling. Open flap surgery should remain the control comparison in these studies.

Methological issues

1. The aim of main studies was to evaluate the efficacy of the whole procedure of tissue reconstruction in periodontal surgery: surgery strategy + bone substitute + collagen membrane. Thus, it is quite difficult to certify that the obtained results can be extended to the collagen membrane alone: the success is charged to the whole procedure in which the collagen membrane takes its part. Knowing this limitation, all studies were used for the performance analysis.

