A new fact is defined as any new safety data which may lead to a reassessment of the relationship between the benefits and risks balance of the research or the product being investigated, changes in the use of the product, the conduct of the research or documents relating to the search, or to suspend or interrupt or modify the protocol of the search or similar searches. (R.1123-46 of the French Public Health Code).

In the case of a new medical fact, the Sponsor, will be responsible for reporting new facts to the authorities in accordance with national regulations, as follows:

- Inform without delay the ANSM about the new medical fact, at the following email address: [contact] with the following subject: Fait nouveau / trial number/ international non-proprietary name (INN) or substance code and including:
 - - ID-RCB N°,
 - - Title of the study protocol,
 - - Protocol code number,
 - - Summary of the new fact and urgent safety measures implemented if necessary,
 - All relevant information for the evaluation of the new fact.
- Inform without delay the director of the Agence Régionale de Santé (ARS; regional health agency) and the Ethical Committee (CPP).

Any follow-up information with regards to the new safety medical fact will be reported to the regulatory authorities within 8 calendar days, and details regarding the urgent safety measures set up will be sent within 15 days to the regulatory authorities.

VIII. STATISTICAL ASPECTS

VIII.1. SAMPLE SIZE DETERMINATION

As the study is descriptive, the calculation of study size is not calculated based on considerations relating to formal hypothesis tests. The required number of patients is calculated to guarantee that the endpoints associated with the main objective of the study could be estimated with sufficient precision.

The choice of a target of 90% of patients with tissue and bone regeneration at 12 weeks post-surgery is based on an estimation of the kinetics of reconstruction according to the literature (similar products resorbable membrane but with or without filling with different bone substitute) [3, 5, 10, 11, 17, 18, 20]. The score will be from 88.8% to 100% with follow-up from 4 to 12 months (due to evaluation of the bone void filler and not only the collagene membrane).

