For the primary endpoint of effectiveness as measured by the performance of the RCM (binary endpoint) with a 90% target frequency (as hypothesized) and a confidence level of 95%, the following precisions can be achieved. The calculation was made using SAS[®].

Precision	Target frequency of performance	Number of patients to evaluate	Number of patients to recruit
8.3%	90%	50	56
6.8%	90%	75	83
5.9%	90%	100	111
5.3%	90%	125	139
5.0%	90%	150	165

Table 2 Sample size determination

With 50 patients, a precision around 8.3% can be achieved.

Accounting for a maximum of 10% dropouts or missing data, 56 patients should be recruited in the cohort.

VIII.2. ANALYSIS SETS

Four populations will be defined:

- Screened population will include all patients entering the study,
- Safety Set (SS) population will include all patients who received the RCM product,
- Full Analysis Set (FAS) efficacy population will include all patients who received the RCM product and in whom at least one efficacy information has been collected after the application of the RCM,
- Per-Protocol (PP) efficacy population will include all patients in FAS population without any major protocol deviation.

Remark: according to the ICH E9 recommendations, this subset of patients corresponds to a subset of the full "intention-to-treat" analysis set (including all randomized patients), being the full analysis set (FAS).

VIII.3. MISSING VALUES AND DROP-OUT

For the primary analysis (FAS analysis), a patient with missing data on the one of primary efficacy endpoint (swelling, wound closure or colour of the implantation site) will be considered as non efficacy of the product for this patient. Sensitivity analyses will be performed according to the following scenarios:

- No missing data will be imputed
- The missing data for the one of primary efficacy endpoint (swelling, wound closure or colour of the implantation site) will be considered as efficacy of the product.

VIII.4. STATISTICAL ANALYSIS

VIII.4.1. GENERAL CONSIDERATION

A Statistical Analysis Plan will be written by the biostatistician detailing the statistical analysis. The document will constitute the reference document as far as statistical analyses and methodologies are concerned. This document will be approved and signed by the Sponsor and the Principal Investigator before the first database lock.

The statistical analysis will be performed on SAS® version 9.4 or later (or equivalent statistical software).

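### The literature range in VIII.1 disagrees with Table 1, and ±8.3%, the only precision given for 50 patients, is narrower than the planned exact limits give at 90% and at the lower rates in Table 1

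*Combined protocol and SAP*

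**What the plan says.** Section VIII.1 sizes the study on precision alone; there is no hypothesis test. It introduces "The choice of a target of 90% of patients with tissue and bone regeneration at 12 weeks post-surgery" as resting on references "3, 5, 10, 11, 17, 18, 20" and gives the range of their results: "The score will be from 88.8% to 100% with follow-up from 4 to 12 months". It attributes that follow-up period to the evaluation of the bone filler rather than of the membrane alone.

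The same seven references are tabulated in II.2 under the caption "Table 1 Justification of the percentage of soft tissue healing". The entries are 100, 88.5, 100, 100, 81.2, 89.5 and 87%.

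The precision is then calculated "with a 90% target frequency (as hypothesized) and a confidence level of 95" per cent, and the results are set out in "Table 2 Sample size determination". Every row of that table uses 90%; only the number of patients varies. The conclusions drawn are "With 50 patients, a precision around 8.3% can be achieved" and "Accounting for a maximum of 10% dropouts or missing data, 56 patients should be recruited in the cohort". The synopsis repeats ±8.3% for 50 patients without naming the rate at which it applies.

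For the analysis, the synopsis and VIII.4.1 both specify exact confidence limits for percentages.

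**The concern.** Two things do not fit together. First, the stated range of the supporting literature cannot be obtained from the protocol's own table of that literature: its lower end is 7.6 points above the table's minimum (88.8 − 81.2). Secondly, the precision promised for 50 patients is not the precision of the interval that will be reported.

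Precision is the only property the design claims, so it should be described correctly. The literature range is the reader's main guide in VIII.1 to how far the true rate might sit from 90%, and Table 2 shows nothing at any other rate. Someone relying on VIII.1 would expect rates no lower than about 89% and an interval of about 8 points either side. At the lower rates in Table 1 the reported interval will be wider than that, and its lower side is the longer one.

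**Working it through.** **1. The range.** The Table 1 values, matched to the reference list, are [20] 100; [3] 88.5; [5] 100; [11] 100; [17] 81.2; [18] 89.5; [10] 87.

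- Minimum 81.2%, maximum 100%.
- Below 88.8%: 88.5, 87 and 81.2, so three of seven. The value 88.8 does not occur.
- Median 89.5%; unweighted mean 646.2/7 = 92.3%. A planning rate of 90% is therefore a central value.

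**2. The plan's own figures.** The normal-approximation half-width is 1.96 × √(p(1 − p)/n). With p = 0.90 and n = 50:

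1.96 × √(0.09/50) = 1.96 × 0.0424 = 0.0832, or ±8.3 points.

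Allowing for 10% loss, 50/0.9 = 55.6, so 56. Both figures reproduce.

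**3. The same case by the planned method.** Exact (Clopper-Pearson) limits for x successes in n are the 2.5% point of Beta(x, n − x + 1) and the 97.5% point of Beta(x + 1, n − x). For 45/50 they are 78.2% and 96.7%.

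- Half-width: 9.2 points.
- Lower limit 11.8 points below the estimate; upper limit 6.7 points above it.

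**4. Other rates, n = 50.** Exact limits need whole counts, so each Table 1 rate is paired with a nearby count (87% of 50 is 43.5, taken as 44).

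| Rate | Normal approx. half-width | Count | Exact 95% limits | Exact half-width | Lower limit below estimate |
|---|---|---|---|---|---|
| 81.2% | 10.8 | 41/50 (82%) | 68.6% to 91.4% | 11.4 | 13.4 |
| 87%; 88.5% | 9.3; 8.8 | 44/50 (88%) | 75.7% to 95.5% | 9.9 | 12.3 |
| 90% | 8.3 | 45/50 (90%) | 78.2% to 96.7% | 9.2 | 11.8 |
| 100% | 0 (degenerate) | 50/50 (100%) | 92.9% to 100% | 3.6 | 7.1 |

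The interval widens below 90% and narrows above it.

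**5. The other rows of Table 2.** The formula in step 2 and n/0.9 to the nearest whole number give:

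| n | Half-width | Printed | n/0.9 | Printed |
|---|---|---|---|---|
| 75 | 6.79 | 6.8 | 83.3 | 83 |
| 100 | 5.88 | 5.9 | 111.1 | 111 |
| 125 | 5.26 | 5.3 | 138.9 | 139 |
| 150 | 4.80 | 5.0 | 166.7 | 165 |

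Only the 150-patient row departs from the others. It should read 4.8% and 167; the printed 165 equals 150 × 1.1.

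**The case against.** **The range is not an input.** This stands. The calculation uses 90%, not 88.8%. Correcting the range changes neither ±8.3% nor 56, and 90% remains a reasonable centre for the tabulated results.

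**The two ranges may describe different things.** VIII.1 speaks of tissue and bone regeneration and of follow-up from 4 to 12 months; Table 1 speaks of soft tissue healing and gives no follow-up. By their titles, the 87% source reports 30 months after loading and the 89.5% source reports 4 years. This stands as a caution about the fix: putting 81.2% into the sentence while keeping its follow-up wording could misstate the sources. It does not remove the discrepancy. VIII.1 cites all seven references and announces no selection, and the 88.5% source, titled as 1-year post-loading results, is already below 88.8%. If 88.8 is a slip for 88.5, then 87 and 81.2 are still left out.

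**±8.3% is offered as approximate and conditional on 90%.** That is fair for VIII.1, less so for the synopsis, which names no rate. Planning with a normal approximation is also ordinary practice. It remains true that the interval to be reported is a different and wider one at that same rate.

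**Stronger readings that the documents do not support.** A reader might infer that ±8.3% is the favourable end of what 50 patients can deliver. It is not: the interval narrows above 90%, and three of the seven sources report 100%, so ±8.3% is an intermediate figure. A reader might also infer that 50 patients are too few. VIII.1 asks for sufficient precision but sets no limit that a wider interval would breach.

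**Conclusion.** The point holds as a correction to the sizing rationale, not to the sample size. The range in VIII.1 contradicts Table 1 for the same references, with three of seven values below the stated minimum. Separately, the stated precision understates the width of the planned interval: at 45/50 the half-width is 9.2 rather than 8.3 points and the lower arm is 11.8 points. At 41/50 these become 11.4 and 13.4. The method mismatch exists at 90% whatever the literature range; the range matters because it hides how far the rate might plausibly fall below 90%.

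This rests on reading the exact method as Clopper-Pearson, on 50 evaluable patients, and on Table 1 being the evidence that VIII.1 summarises, as the identical reference list indicates. The sources themselves were not available, so the reason for 88.8% cannot be settled here. The 150-patient row of Table 2 is wrong by its own method, but it was not chosen and affects nothing in the study.

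**What to change.** 1. In VIII.1, reconcile the literature range with Table 1 (81.2% to 100%), or state which references and which follow-up the narrower range covers. If 81.2% is adopted, check the 4-to-12-month wording against the sources at the same time.
2. In VIII.1 and the synopsis, restate the precision for 50 evaluable patients with the planned exact limits at several rates on both sides of 90%: 41/50, 68.6% to 91.4%; 44/50, 75.7% to 95.5%; 45/50, 78.2% to 96.7%; 50/50, 92.9% to 100%. If ±8.3% is kept, label it as the normal approximation at 90%.
3. In Table 2, change the 150-patient row to 4.8% and 167 (minor).

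These are wording changes. They need no additional patients and leave 50 evaluable and 56 recruited as they are. The only cost is a slightly less favourable stated precision.

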Secondary measures outcomes Time points at which the secondary outcomes measures are assessed Inclusion criteria Exclusion criteria	follow-up, especially the one mentioned in the Instructions For Use (IFU) such as post-operative infections, discomfort, irritation, fever, inflammatory reaction and allergy. - Radiographic examination of periodontal tissues. Safety data: From screening throught visit at 12 weeks (± 1 week). X-Rays measurements: - Pre-surgery - 12 weeks post-surgery (± 1 week) - Male or female aged from 18 to 70 - Periodontal defects (e.g. cyst, bone tumour, crest augmentation) - Alveolar bone defect after tooth (teeth) extraction - Non Opposition form (consent of the patient) - Patients affiliated to the French social security - Patients not under guardianship or judicial protection - Pregnancy or breastfeeding women - Severe smoker (>10 cigarettes per day) [13] - Acute infections - Allergies to the material (if an allergy of any kind is suspected, adequate exams must be carried out in advance) - Refusal of the patient to adhere to surgical follow-up and to the limit in	

	activity level - Fever and/or local inflammation - HIV positive known - History of uncontrolled diabetes (untreated or not stabilized by treatment)				
	- History of treatments for previous corticosteroids, long-term (more the months) and interrupted for less than 3 months				
	- History of chemotherapy in progress or during the last three months				
	- History of cervico-facial radiotherapy				
	- History of bone disease with disorders of blood circulation which is defined				
	as Albers-Schönberg disease or Paget's disease				
	- Known severe hyperparathyroidism				
	- History of severe immune deficiency				
	A sample size of 50 patients would give with 95% confidence interval a				
Study size	precision of $\pm 8.3\%$.				
Study Size	Accounting for a maximum of 10% of dropouts or missing data, 56 patients				
	should be recruited in the cohort.				
	- Duration of the inclusion period: 18 months				
Duration of the research	- Duration of follow-up per participant: 12 weeks (±1 weeks)				
	- Total duration of the research project: 22 months				
	A Statistical Analysis Plan (SAP) will be written by the Biostatistician of the CRO in charge of the study. This document will be approved and signed by the Sponsor, the Coordinating Investigator and the clinical expert before the first database lock.				
	All data will be presented using descriptive statistics.				

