Quantitative variables will be described by the number of values entered, the number of missing data, the mean, the standard deviation, the 95% CIs for the means, the median, the 1st and 3rd quartiles, the minimum and maximum.

Qualitative variables will be described by the number of data filled in, the number of missing data, the frequency and the percentage of each modality. The 95% CIs of the percentages will be performed using exact confidence limits method.

All variable in the database will be described using descriptive statistics and all individual data will be presented in listings.

An interim analysis is planned in this study protocol in order to obtain the first results for December 2019. No sub-group analysis is planned.

VIII.4.2. ANALYSIS OF THE PRIMARY ENDPOINT

The primary endpoint analysis will be performed on FAS population. The primary endpoint will be analyzed on the PP population if the difference in the number of subjects between FAS and PP is more than 10%.

The primary efficacy endpoint is the mucosa aspects reported by swelling, wound closure and colour.

The composite primary endpoint will be summarized using descriptive statistics with binary outcome.

For patients who do not have swelling on the surgical site, with a complete wound closure on the surgical site and pink colour or identical colour to the surrounding mucosa on the surgical site, the investigational product will be considered as efficacious. If at least one of the primary endpoint performance is not satisfied, the investigational product will be considered ineffective for the patient.

Sensitivity analyses using different analyses sets and missing data handling as described above will be performed (see section "Missing values / dropouts"). The PP analysis will be considered as confirmatory analysis.

VIII.4.3. SAFETY ANALYSES

The safety analysis will be performed on SS population.

Safety endpoints will be AEs and SAEs all through the study.

AEs will be coded using MedDRA dictionary (latest version available). AEs will be classified according to period of occurrence: pre-treatment AEs and Treatment-Emergent AEs.

- Pre-treatment AEs are defined as adverse events occurring before the introduction of the investigational product.
- Treament-Emergent AEs are defined as an adverse who that emerges after introduction of the investigational product having been absent pre-treatment, or worsens relative to the pre-treatment state.

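### The ±8.3% precision stated for 50 patients is not that of the exact limits the plan prescribes: at 45/50 the exact 95% CI is 78.2% to 96.7%

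*Combined protocol and SAP*

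**What the plan says.** Section VIII.1 disclaims any hypothesis test and says the number of patients "is calculated to guarantee that the endpoints associated with the main objective of the study could be estimated with sufficient precision". For the binary primary endpoint, "with a 90% target frequency (as hypothesized) and a confidence level of 95%, the following precisions can be achieved", and the section then gives Table 2. On method it says only "The calculation was made using SAS"; no formula or interval type is named. For the chosen size: "With 50 patients, a precision around 8.3% can be achieved". Recruitment follows: "Accounting for a maximum of 10% dropouts or missing data, 56 patients should be recruited in the cohort".

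The synopsis (Study size) repeats the claim without any qualifier: "A sample size of 50 patients would give with 95% confidence interval a" precision of ±8.3%.

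For the analysis, Section VIII.4.1 and the synopsis (Statistical analysis of the data) both say: "The 95% CIs of the percentages will be performed using exact confidence limits method". Section VIII.4.2 summarises the composite primary endpoint as a binary outcome, so this rule covers its percentage.

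**The concern.** The precision used for planning and the interval prescribed for reporting come from different methods, and the plan does not say so. For a proportion near 90% with 50 patients the difference shows. The exact interval is wider than the normal approximation, and it is asymmetric, with the longer arm on the lower side.

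Precision is the only stated basis for the study size. The confidence interval is also the main inferential result of a single-arm descriptive study, and readers of a performance claim look first at its lower limit. Someone who reads ±8.3% around 90% expects a lower limit of 81.7%. The trial could meet its 90% target exactly and still report a lower limit clearly below that.

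**Working it through.** **Inputs.** Success proportion 0.90, confidence level 95%, evaluable sizes 50 to 150, and the stated precisions and recruitment numbers: Section VIII.1 and Table 2. Two-sided limits: inferred from the ± in the synopsis. Exact limits for percentages: Section VIII.4.1. Assumption: exact means Clopper-Pearson.

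**1. The plan's own figure.** The normal-approximation half-width is 1.96 × √(p(1−p)/n). At p = 0.90 and n = 50 this is 1.96 × √(0.09/50) = 8.32 points, which reproduces the stated 8.3.

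**2. The exact interval at the same point.** The Clopper-Pearson lower limit is the 2.5th percentile of Beta(x, n−x+1), and the upper limit is the 97.5th percentile of Beta(x+1, n−x). With x = 45 and n = 50:

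- lower limit 78.19%, upper limit 96.67%
- half-width (96.67 − 78.19)/2 = 9.24 points
- arms: 90 − 78.19 = 11.81 below and 96.67 − 90 = 6.67 above

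**3. Comparison with the stated ±8.3.**

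- Half-width: 9.2 against 8.3, a gap of 0.9 point, or about 11% wider (9.2/8.3 = 1.11).
- Lower limit: 78.2% against 90 − 8.3 = 81.7%, which is 3.5 points lower.
- Upper limit: 96.7% against 90 + 8.3 = 98.3%, which is 1.6 points lower.

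**4. All rows of Table 2.** Where 90% of n is not a whole number, the two bracketing counts are shown.

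| n | Stated | Normal approximation | Exact half-width |
|---|---|---|---|
| 50 | 8.3 | 8.32 | 45/50: 9.24 |
| 75 | 6.8 | 6.79 | 67/75 (89.3%): 7.61; 68/75 (90.7%): 7.23 |
| 100 | 5.9 | 5.88 | 90/100: 6.36 |
| 125 | 5.3 | 5.26 | 112/125 (89.6%): 5.74; 113/125 (90.4%): 5.55 |
| 150 | 5.0 | 4.80 | 135/150: 5.13 |

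The first four rows match the normal approximation. Jeffreys half-widths (8.31, 6.79, 5.88, 5.26) match the same four, so the table alone does not show which method was used. No row matches the exact values shown.

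**5. Other readings of exact.** Mid-P limits at 45/50 are 79.2% to 96.2%, a half-width of 8.5. The gap shrinks to 0.2 point, but this is still not 8.3.

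**6. If more than 50 are analysed.** The full analysis set keeps treated patients "in whom at least one efficacy information has been collected after the application of the RCM", so up to 56 may be analysed. The exact half-width is 8.9 at 50/56 (89.3%; 78.1% to 96.0%) and 8.3 at 51/56 (91.1%; 80.4% to 97.0%). The lower arms remain long: 89.3 − 78.1 = 11.2 and 91.1 − 80.4 = 10.7 points.

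**7. The 150 row.** The formula behind the other rows gives 4.8, not 5.0. The other recruitment numbers are n/0.9 rounded to the nearest whole number (55.6, 83.3, 111.1 and 138.9 give 56, 83, 111 and 139). For 150 this is 166.7, so 167. The stated 165 equals 150 × 1.1.

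**The case against.** The strongest reply is that 8.3 is a correct normal-approximation half-width, that planning with a symmetric approximation and reporting exact limits is common, and that the plan nowhere says Table 2 used exact limits. This stands as far as it goes: the only slip in calculation is the 150 row. It does not remove the mismatch, because the synopsis ties ±8.3% to a 95% confidence interval and the same synopsis prescribes another kind of interval.

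A second reply is that nothing turns on the figure. The study is descriptive, sufficient precision is given no numerical meaning, no 8.3-point target is failed, and Section VIII.1 presents the figure as approximate (the synopsis does not). This also stands, and it keeps the point small.

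Third, 45/50 is a single outcome, with a probability of about 18% if the true rate is 90%. Averaged over a binomial distribution with n = 50 and p = 0.90, the exact half-width is 9.02, so the like-for-like gap is 0.7 point. That is fair, and the conclusion is unchanged. Quoting both arms remains useful because a ± figure hides the asymmetry.

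Fourth, the results for 56 patients depend on how missing data fall. Section VIII.3 counts a missing component as failure in the full analysis set. If the whole 10% allowance were missing data within that set, 45 successes would be 45/56 = 80.4%, and the half-widths of 8.9 and 8.3 would not apply. Those two figures hold only if about 90% of all 56 succeed after that rule.

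Finally, restating rows for sizes that will not be used is more than is needed to judge 50 patients. Naming the method and giving the exact interval at 45/50 is the essential part; the rest keeps the table consistent.

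**Conclusion.** The concern holds. The stated precision of 8.3% for 50 patients is not that of the exact limits the plan prescribes. At the hypothesised 90%, the exact 95% interval is 78.2% to 96.7%, with a half-width of 9.2 rather than 8.3 and a lower limit 3.5 points below the one implied. This is a mismatch between planning and analysis methods, not a miscalculation of 8.3.

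The size is modest and rests on reading exact as Clopper-Pearson; under mid-P the half-width gap would be only 0.2 point. It does not call the choice of 50 evaluable and 56 recruited patients into question, but the sole stated justification for that choice should describe the interval that will be reported. The 150 row is a separate, minor inconsistency.

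**What to change.** Keep 50 evaluable and 56 recruited patients and the exact limits in the analysis. Then:

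- In Section VIII.1 and the synopsis, replace the 8.3% statement with: *with 45 successes in 50 analysed patients, the exact (Clopper-Pearson) 95% confidence interval is 78.2% to 96.7%*. If another exact method is meant, name it and give its limits instead.
- Name the interval method under Table 2, and use the same name in Section VIII.4.1 and in the separate analysis plan announced there.
- Restate the precision column on exact limits: 45/50, 9.2; 67/75 and 68/75, 7.6 and 7.2; 90/100, 6.4; 112/125 and 113/125, 5.7 and 5.6; 135/150, 5.1. Show the actual percentage beside each count that is not exactly 90%.
- Bring the recruitment number in the 150 row into line with the other rows: 150/0.9 = 167.

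The cost is wording in Section VIII.1, Table 2 and the synopsis, plus the method name in Section VIII.4.1. No patients are added and the analysis does not change; the stated precision becomes slightly less favourable.

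### The ±8.3% that justifies 50 evaluable patients is a normal-approximation figure; the planned exact interval is wider, and VIII.1 does not say whether the 90% already allows for missing counted as failure

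*Combined protocol and SAP*

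**What the plan says.** **Basis of the sample size (VIII.1).** No hypothesis test is used. The number of patients is chosen so that "the endpoints associated with the main objective of the study could be estimated with sufficient precision". The planning rate is "a target of 90% of patients with tissue and bone regeneration at 12 weeks post-surgery". Table 2 pairs a precision of 8.3% with 50 patients to evaluate and 56 to recruit, and the text adds: "With 50 patients, a precision around 8.3% can be achieved". On losses it says: "Accounting for a maximum of 10% dropouts or missing data, 56 patients should be recruited in the cohort". The synopsis (Study size) repeats the 50, the ±8.3% and the 56. VIII.1 says that the calculation was done in SAS but names no interval method.

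**Primary analysis (VIII.2 to VIII.4.2).** "The primary endpoint analysis will be performed on FAS population". The FAS holds patients who received the membrane and "in whom at least one efficacy information has been collected after the application of the RCM". Under VIII.3, a FAS patient who lacks swelling, wound closure or colour "will be considered as non efficacy of the product for this patient". Leaving missing values unimputed, and counting them as success, are sensitivity analyses.

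**Intervals (VIII.4.1 and synopsis).** 95% intervals for percentages use exact limits.

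**Whose 90% (II.3).** The hypothesis is stated over patients who undergo the procedure with the membrane, assessed at 12 weeks.

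**The concern.** Precision is the only reason given for 50 evaluable and 56 recruited patients, so the quoted precision should describe the interval that the report will contain. It may fail to do so in two ways.

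1. The half-width appears to come from a different interval method from the one planned for the report.
2. The 50 is what remains after patients with missing data are taken out, but the primary analysis keeps such patients, if they are in the FAS, in the denominator as failures. VIII.1 does not say whether the 90% already includes those failures.

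At stake is how a reader judges the result. Someone who expects 90% with about 8 points either side may misread a lower primary rate or a longer lower arm as a shortfall of the device, when part of it comes from the interval method or the missing-data rule.

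**Working it through.** **Inputs.** Rate 90%, confidence 95%, n = 50 to evaluate, 56 to recruit, at most 10% lost (VIII.1, Table 2). Exact limits (VIII.4.1). FAS with missing counted as failure (VIII.2, VIII.3, VIII.4.2).

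**Step 1: reproduce the plan's figure.** Wald half-width = 1.96 × √(p(1 − p)/n).
- n = 50: 1.96 × √(0.90 × 0.10/50) = 8.32 points, stated as 8.3.
- n = 75, 100, 125: 6.79, 5.88, 5.26, stated as 6.8, 5.9, 5.3.
- n = 150: 4.80, stated as 5.0. This row does not match, but it is not the one used.

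Other methods at n = 50 give 9.3 (Wald with continuity correction), 8.5 (Wilson) and 9.2 (exact, mean of the two arms). Only the plain Wald formula gives 8.3. The method is thus inferred from the numbers.

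Recruitment: 50/0.9 = 55.6, rounded up to 56, as stated.

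**Step 2: the planned interval with no missing data.** Clopper-Pearson limits for x successes in n are the 2.5% quantile of Beta(x, n − x + 1) and the 97.5% quantile of Beta(x + 1, n − x). For 45/50 they are 78.2% and 96.7%.
- Below the estimate: 90.0 − 78.2 = 11.8 points. Above it: 96.7 − 90.0 = 6.7 points.
- Mean half-width 9.2 against the stated 8.3; total width 18.5 against 2 × 8.3 = 16.6.

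This step needs no assumption about missing data.

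**Step 3: missing counted as failure.** Assume that 90% applies to observed patients and that all 56 are in the FAS. With m missing, expected successes are 0.9 × (56 − m): 50.4, 47.7, 45.9 and 45.0 for m = 0, 3, 5 and 6. The nearest whole counts give:

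| Missing in FAS | Successes/56 | Rate | Exact 95% limits | Mean half-width |
|---|---|---|---|---|
| about 0 | 50 | 89.3% | 78.1% to 96.0% | 8.9 |
| about 3 | 48 | 85.7% | 73.8% to 93.6% | 9.9 |
| about 5 | 46 | 82.1% | 69.6% to 91.1% | 10.7 |
| 6 (limiting case) | 45 | 80.4% | 67.6% to 89.8% | 11.1 |

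Five of 56 is 8.9%, the most within the 10% maximum. Six of 56 is 10.7%, just over it, but it is Table 2's own split of 50 from 56. In that limiting case, success in all 50 observed patients would still give only 50/56 = 89.3%.

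**Step 4: the other readings.** If all six losses fall outside the FAS, the result is 45/50 and Step 2 applies unchanged. If 90% is the rate over all treated patients, failures through missing data are already inside it. The fall in Step 3 then does not arise, and only the difference in interval method remains.

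**The case against.** - **The 90% may already be the FAS rate.** II.3 states it over patients treated with the membrane, and VIII.1 attaches it to the primary endpoint. This stands as a fair reading. VIII.1 also removes dropouts or missing data to reach the 50, which supports the other one. The text is ambiguous.
- **The interval-method gap is small.** It is under one point on the mean half-width, VIII.1 says only that the precision is around 8.3%, and a normal approximation at the planning stage is common. True, and it limits the weight of the point. The lower arm is nonetheless 11.8 points, and the planned method could have been used for planning at no cost.
- **Some exact intervals come close.** Exact limits for 51/56 are 80.4% to 97.0%, a mean half-width of 8.33. So it cannot be said that no planned interval has that width. But that is a 91.1% rate on 56 patients, with 10.7 points below, not 90% on 50.
- **The size of the missing-data effect is unknown.** The 10% is a maximum, V.4 asks staff to complete assessments after withdrawal, and patients with no efficacy item after application leave the FAS. All of this stands, so Step 3 is a range and not a forecast.
- **The planned outputs will show the effect.** VIII.3 includes no imputation and missing as success, and counts of missing data and listings are planned. They show the effect once data are in; they do not correct the precision stated in advance.

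A reader might infer that the primary rate is bound to fall to 80% to 82%, that the study is too small, or that counting missing as failure is wrong. The documents support none of these. The fall depends on a reading of the 90% and on FAS membership that they leave open, there is no test or pass mark that 56 patients could fail, and missing as failure is a defensible conservative rule.

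**Conclusion.** The point holds as a minor one. The only figure that justifies the sample size does not describe the interval that the plan will report: ±8.3 is a Wald half-width, while the exact interval at 45/50 is 78.2% to 96.7%. That part rests only on inferring the method from the table.

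The second part is conditional. If 90% is the rate among observed patients and all 56 are in the FAS, the expected primary result runs from about 89.3% (78.1% to 96.0%) with no missing data to 82.1% (69.6% to 91.1%) with about five missing, and to 80.4% (67.6% to 89.8%) in the limiting case of six. If either assumption fails, the effect shrinks or disappears. The documents do not settle which reading applies, or how many losses stay in the FAS.

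Because the study is descriptive, what changes is the stated precision and how the estimate is read against 90%. No test or decision rule is involved.

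**What to change.** 1. In VIII.1 and the synopsis, replace ±8.3%, or qualify it as a normal approximation, and give the planned exact 95% interval at 45/50: 78.2% to 96.7%.
2. In VIII.1, state whether 90% is the expected rate among observed patients or among all FAS patients. If among observed patients, add the four whole-count rows from the table above (50, 48, 46 and 45 of 56) as the expected results of the primary analysis, with the assumption that all 56 are in the FAS. Note that patients outside the FAS are not counted as failures.
3. Keep the missing-as-failure rule, the 90% target and the 56 patients.

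The cost is a few sentences, with no extra patients, data or analyses. The downside is that the stated precision looks slightly less favourable.
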